Study Schedule:	
June 2019: planned start of measurements
 
December 2020: planned end of measurements

Investigator(s):	
Examiner
 
 - [name]^{1,2,3} - [name]^{1,2,3} - [name]^{1,2} - [name].¹ 
1.) University of Applied Sciences and Arts Southern Switzerland, Department of Business Economics, Health and Social Care, Physiotherapy Graubünden, [name]
 
2.) THIM the International University of Physiotherapy, [name]
 
3.) Vrije Universiteit Brussel, Department of Movement and Sport Sciences, [name]
 
Contact / Director of Studies [name], PhD University of Applied Sciences and Arts Southern Switzerland Department of Business Economics, Health and Social Care Physiotherapy Graubünden [name] [contact] [contact]

Study Centre(s):	
Single Centre Study:
 
University of Applied Sciences and Arts Southern Switzerland Physiotherapy Graubünden [name]

SUPSI

Statistical Considerations:
	
Psychophysiological changes between terrestrial altitude and normobaric hypoxia - a randomized clinical trial.
 
Repeated measures analysis of variance (MANOVA)
 
2 Factors (Physiological Parameters)
 
 - Situation (terrestrial altitude vs. simulated altitude) - Time (baseline, after step-up task, 0, 5, 10, 15, 20, 25, 30 min post-cold water immersion of the hand) 
2 factors (psychological parameters, balance, thermal comfort, temperature perception)
 
 - Situation (terrestrial altitude vs. simulated altitude) - Time (baseline, post-cold water immersion of the hand) - 
The significance level is set at $P < 0.05$, and the statistical data analysis is carried out with SPSS V. 26.

GCP Statement:
	
This study will be conducted in compliance with the protocol presented here, the current version of the Declaration of Helsinki, the ICH-GCP, ISO EN 14155 (where applicable), and the Swiss Human Research Ordinance HFV.

SUPSI

Overview of the study

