4 STUDY OBJECTIVES

4.1 General objectives

The aim of this study is to evaluate and compare the psychophysiological changes during terrestrial and simulated altitude. These changes will be investigated after a 5-minute step-up task and after a 5-minute cold water immersion of the hand in a) a normobaric, normoxic situation, b) normobaric, hypoxic situation and c) hypoxic, hypobaric situation.

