8.2.1 Experimental intervention

Simulated height: The test subjects are in the laboratory of our institution and are connected to Cloud 9 by means of a mask. The subjects are exposed to a simulated altitude of 3530 m above sea level under normobaric conditions. This intervention is used to determine the psychophysiological effect under normobaric and hypoxic conditions.

Terrestrial altitude: The subjects are at an SAC hut (Bergrestaurant Hohsaas: <https://www.hohsaas-bergrestaurant.ch>) in the canton of Valais at an altitude of 3200 m above sea level. By means of this

SUPSI

exposure, the psychophysiological effect under hypobaric and hypoxic conditions is determined. The test subjects spend a single night in this SAC hut and the measurements are repeated the next day.

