8.2.2 Control intervention

Control: The test subjects are in our laboratory under normobar and normoxic conditions. This situation serves as a control intervention, which is contrasted with the simulated and terrestrial situation.

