
Blood Pressure & Heart Rate Skin temperature Lactate & Creatine Kinase
 
10 min
 
3.) Cold water immersion of the hand
 
5 min
 
4.) Follow-up Perfusion Microcirculation Oxygen Saturation Muscle & Brain Oxygen saturation of blood Blood Pressure & Heart Rate Skin temperature Lactate & Creatine Kinase Balance measurement Pain sensation Psychological measurements Thermal comfort & temperature perception
 
40 min
	
Skin temperature Lactate & Creatine Kinase
 
10 min
 
3.) Cold water immersion of the hand
 
5 min
 
4.) Follow-up Perfusion Microcirculation Oxygen Saturation Muscle & Brain Oxygen saturation of blood Blood Pressure & Heart Rate Skin temperature Lactate & Creatine Kinase Balance measurement Pain sensation Psychological measurements Thermal comfort & temperature perception
 
40 min
	
Skin temperature Lactate & Creatine Kinase
 
10 min
 
3.) Cold water immersion of the hand
 
5 min
 
4.) Follow-up Perfusion Microcirculation Oxygen Saturation Muscle & Brain Oxygen saturation of blood Blood Pressure & Heart Rate Skin temperature Lactate & Creatine Kinase Balance measurement Pain sensation Psychological measurements Thermal comfort & temperature perception
 
40 min

---	---	---

Test log	Time exposure	Visits
Declaration of Consent	30 min	Unique
Simulated Height	20 + 90 min = 110 min	Unique
Terrestrial Altitude	20 + 90 min = 110 min	Twice (incl. 1x overnight stay)
Control intervention	20 + 90 min = 110 min	Unique
TOTAL TIME COMMITMENT	470 min + 1 night	

Each test subject can expect a total time expenditure of 470 minutes excluding the journey to and from Valais and the overnight stay at the SAC mountain hut.

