2.2 Intervention

The subject is then exposed to either the simulated altitude or the normobaric & normoxic situation. Afterwards, a step-up task of 5 minutes and a cold water bath immersion of the hand for 5 minutes is performed. In the terrestrial situation, the subject is measured at the time of arrival at the SAC Hut, as well as the following day after an overnight stay at the SAC Hut. The experimental procedure is therefore illustrated:

[figure not shown]

Illustration of the experimental process

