Altitude sickness symptoms, which are very often studied in this field of research, showed the following differences: The risk or development of altitude sickness seems to be greater at terrestrial altitude compared to simulated altitude (Loeppky et al. 2005, Miyagawa et al. 2011). The difference between terrestrial altitude and simulated altitude on sleep quality was also investigated. In both initial positions, oxygen transport is significantly suppressed during the sleep phase. However, the simulated height in this case is a continuous (during the sleep phase) situation (Berssenbrugge et al. 1983). Millet et al. (2012), on the other hand, described that the ventilation of the lungs, and consequently the CO₂ content in the blood, are lower at the terrestrial altitude, compared to the simulated altitude. Poor sleep at terrestrial altitude could also have a negative effect on the daily state of mind as well as on drowsiness. Furthermore, the reduced oxygen saturation or the increased CO₂ content in the arterial blood could

SUPSI

lead to a reduction in oxygen saturation in the muscles and brain (and reduced cognitive performance) in the terrestrial situation. However, it must be explicitly mentioned that a direct comparison can only be made here if the simulated and also the terrestrial altitude are carried out in the same amount of time.

Thermal comfort and temperature perception are largely dependent on the outside temperature. The room temperature in the SAC hut is therefore adapted as much as possible to the conditions of the laboratory in order to keep this disturbing factor as low as possible. However, the different temperature in the 2 scenarios could also have an impact on the perfusion of the skin's microcirculation. Furthermore, it was described that sympathetic tone is increased at terrestrial altitude compared to simulated altitude. Catecholamines, such as norepinephrine, also seem to be released more frequently at terrestrial altitudes (Mazzeo et al. 1994).

The result of Noel-Jorand et al. 1996 is interesting. These authors described that the sensation of pain is largely dependent on the hypoxia itself and not only on the difference in air pressure. The pain threshold has decreased in this study and sensory discrimination has increased below terrestrial altitude. Hypoxia and the resulting adaptation to the lack of oxygen itself seem to be the main reason for this (Noel-Jorand et al. 1996).

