11.4.2 Primary Analysis

The statistical data analysis will be carried out by [name]. [name] after completion of the data collection of the entire project.

Repeated measures analysis of variance (MANOVA)

2 factors:

Factor 1: Situation (simulated altitude vs. terrestrial altitude)

Factor 2: Time (baseline, after step-up task, 0, 5, 10, 15, 20, 25, 30 min post-cold water immersion of the hand)

Repeated measures analysis of variance (MANOVA)

2 factors:

Factor 1: Situation (simulated altitude vs. terrestrial altitude)

Factor 2: Time (baseline, post-cold water immersion of the hand)

The significance level is set at $P < 0.05$, and the statistical data analysis is carried out with SPSS V. 23.

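### The two-level situation factor does not say which of the two terrestrial sessions it uses, and no planned test includes the control session

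*Combined protocol and SAP*

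**What the plan says.** Section 11.4.2 plans a repeated-measures analysis with two factors. The first is "Factor 1: Situation (simulated altitude vs. terrestrial altitude". The second is time, with nine levels for the physiological outcomes and two for the others. The synopsis gives the same two-level factor, "Situation (terrestrial altitude vs. simulated altitude", and every hypothesis in section 11.1 sets simulated against terrestrial altitude. Section 11.4.3 states that there is no secondary analysis.

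The design is wider than this. Section 4.1 names three situations: "a) a normobaric, normoxic situation, b) normobaric, hypoxic situation and c) hypoxic, hypobaric situation". Section 8.2.2 says of the control: "This situation serves as a control intervention, which is contrasted with the simulated and terrestrial situation". Terrestrial altitude is measured twice. Section 8.2.1 says "The test subjects spend a single night in this SAC hut and the measurements are repeated the next day", the visit table in section 9.1 lists "Twice (incl. 1x overnight stay", and step 2.2 within section 9.2.2 says that "the subject is measured at the time of arrival at the SAC Hut, as well as the following day after an overnight stay".

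On exposure time, section 11.1 sets a condition: "a direct comparison can only be made here if the simulated and also the terrestrial altitude are carried out in the same amount of time". Later in the same section it accepts that the duration of hypoxia differs between the two scenarios and treats that difference as informative. Sections 6.1.1 and 7.3 randomise only the order of the normoxic control and the simulated-altitude session.

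**The concern.** There are two gaps.

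First, the terrestrial level of the factor has two candidate sessions, which differ by a night at altitude, and the text selects neither. Arrival, next day and their average all comply with section 11.4.2. A choice left open until the data are in can follow the result, and the three options do not estimate the same thing: one is acute exposure, one is exposure after a night, and one is a mixture.

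Second, the control is promised as a comparator and then appears in no test. The hut baseline is taken at altitude, so change from baseline in that session shows the response to stepping and cold water at altitude, not the effect of altitude. The control session is the only normoxic reference for it. If simulated and terrestrial altitude do not differ, the planned analysis cannot say whether both had the same effect or neither had any.

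**Working it through.** **1. Number of sessions.** From the table in section 9.1: consent 30 min, simulated 1 × 110, terrestrial 2 × 110, control 1 × 110. Total 30 + 4 × 110 = 470 min, the stated total. Section 9.2.2 places the measurements on contact days 2 to 5, which is also four.

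**2. The plan's own sample size.** Section 11.2 gives MANOVA, within-between interaction, f(V) = 0.9, alpha 0.05, power 0.6, k = 3 groups, m = 14 measurements, N = 23. With the Pillai-trace noncentral F:

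- s = min(k − 1, m − 1) = 2
- df1 = (k − 1)(m − 1) = 2 × 13 = 26
- df2 = s(N − k − (m − 1) + s) = 2(23 − 3 − 13 + 2) = 18
- λ = N·s·f² = 23 × 2 × 0.81 = 37.26

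Power is 0.647 at N = 23 and 0.586 at N = 22, so 23 is reproduced. (Other noncentrality conventions give 24 or 31.) The calculation therefore assumes three situations, treated as separate groups of people, and 14 measurements. Section 11.4.2 has two situations within the same people and 9 or 2 times.

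**3. Can the named multivariate test take more levels?** With a situations and b times, all within participant, the interaction has p = (a − 1)(b − 1) contrasts and N − p error degrees of freedom. At N = 24 complete participants:

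| Situation levels | 9 times: p, error df | 2 times: p, error df |
|---|---|---|
| 2 (as planned) | 8, 16 | 1, 23 |
| 3 (control plus one terrestrial session) | 16, 8 | 2, 22 |
| 4 (all sessions) | 24, 0 | 3, 21 |

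Only the 4 × 9 case fails; it needs at least 25 complete participants. A univariate repeated-measures analysis of the same interaction has 3 × 8 = 24 and 24 × 23 = 552 df before sphericity correction.

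**4. Cost of the open session choice.** For two tests at 0.05, if independent: 1 − 0.95² = 0.0975. Two sessions in the same people are likely to be positively correlated, which lowers this towards 0.05. The synopsis lists 11 physiological and 6 psychological primary outcomes, 17 in all, and the choice is open for each.

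**5. What is randomised and what is tested.** Four sessions give 4 × 3 / 2 = 6 pairwise comparisons. Section 11.4.2 names one, simulated versus terrestrial, which has two possible terrestrial sessions. The pair with randomised order, control and simulated, is not among the planned tests.

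**6. Period effects.** The position of the hut visit is unclear (step 2.3 within section 9.2.2 does not settle it). Assume that it comes last for everyone. Control and simulated then occupy periods 1 and 2 in either order, arrival is always period 3 and next day always period 4. A model with four situations and four periods has 1 + 3 + 3 = 7 parameters. The situation and period levels fall into three unconnected sets, so the rank is 4 + 4 − 3 = 5. Simulated versus arrival then cannot be separated from period.

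**The case against.** The strongest reply is that section 11.4.2 does what the objectives ask. The primary objectives and all the hypotheses compare simulated with terrestrial altitude, so leaving the control out of the primary test is not in itself an error. That stands. The gap is that sections 4.1 and 8.2.2 commit the study to control contrasts and nothing in section 11 delivers them.

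Three stronger readings are tempting, and the documents do not support them.

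- A reader might infer that the control will never be used. Section 8.2.2 states the intention to contrast it, and section 11.2 assumes three groups. What can be said is that no planned test includes it, which is an internal contradiction.
- A reader might infer that the equal-time sentence in section 11.1 rules out the next-day session. It follows remarks on sleep, carbon dioxide, tissue oxygenation and cognition, and the same section goes on to accept unequal duration. The two statements are in tension; neither yields an analysis rule, so the session remains unnamed.
- A reader might infer that the named method cannot be extended at all. Step 3 shows that only the four-session, nine-time multivariate interaction fails.

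Arrival also cannot serve every outcome. Sleep disorder is a primary outcome, and the hut night comes after the arrival session.

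**Conclusion.** The point holds and should be settled before analysis. One of the two levels of the primary factor is undefined, with up to three versions of the primary test fitting the text. The control contrasts that the protocol promises are not planned, and the only comparison with randomised order is untested.

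The 9.75% figure assumes independent tests and a free choice between two sessions; with positive correlation it is smaller. The zero error df assumes 24 complete participants and nine times. The period result is conditional on the hut visit coming last for everyone, which the documents do not state. The control's share of measurement time, 110 of 440 min, describes participant burden, not inferential harm. No corrected sample size is given, because the documents contain no standard deviations or within-participant correlations.

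**What to change.** - **Section 11.4.2.** Use a linear mixed model, or a sphericity-corrected repeated-measures ANOVA, with Situation at four levels (control, simulated, terrestrial arrival, terrestrial next day), Time, Situation × Time and a participant effect. Name the primary contrast and terrestrial session for each outcome: simulated versus arrival by default, as the session closest in exposure time, and the next-day session for sleep. State the remaining difference in exposure as a limitation.
- **Section 11.4.3.** Replace the present entry with fixed secondary contrasts: simulated versus control, terrestrial arrival versus control, and next day versus arrival. Give a multiplicity rule, or label them supportive.
- **Sequence.** State where the hut visit falls. If it is the same for everyone, fit a period effect only for the randomised laboratory pair, and report the terrestrial contrasts as not separable from period.
- **Alignment.** Bring the synopsis, section 11.1 and section 11.2 into line with this model, including the number of situations and times behind the sample size.

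The cost is protocol wording, somewhat more analysis and more tests to control. No visit is added: all four sessions are already scheduled. The documents do not show that any data had been collected; the protocol is dated May 2019 and measurements were to start in June 2019.

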11.2 Sample size

The sample size in the literature varies. The planned number of 24 subjects is within the wide range and is expedient, time-wise and financially feasible for the study.

The G*Power analysis (V.3.1.) revealed (F-test, MANOVA:repeated measures, within-between interaction, effect size $f(V) = 0.9$, alpha err prob = 0.05, Power (1-beta err prob) = 0.6, number of groups = 3, number of measurements = 14) a required group of 23 participants.

11.3 Criteria for the statistical use of data in the case of incomplete data sets

Only data from subjects who have completed the entire protocol will be included in the study. This ensures that all data has been collected under the same conditions and thus remains homogeneous and comparable.

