11.4 Scheduled analyses

11.4.1 Datasets and Data Population

Only datasets that can be used sensibly will be included in the study. Incomplete data sets that contain only part of the protocol are included in the analysis as far as possible. No new test subject is being sought to replace the missing data.

SUPSI

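### The 2 x 9 repeated-measures MANOVA is complete-case per outcome: one unusable reading of 18 removes the participant from that outcome's analysis, and no available-data method is named

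*Combined protocol and SAP*

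**What the plan says.** Section 11.4.2 names one method, "Repeated measures analysis of variance (MANOVA"), and applies it twice. In both, the first factor is "Factor 1: Situation (simulated altitude vs. terrestrial altitude"). For the physiological outcomes the second factor is "Factor 2: Time (baseline, after step-up task, 0, 5, 10, 15, 20, 25, 30 min post-cold water immersion of the hand"), which is nine times. For the other set it is "Factor 2: Time (baseline, post-cold water immersion of the hand"), which is two times. The synopsis gives the same structure and assigns the psychological measures, balance and thermal ratings to the two-time set. Section 11.4.3 states that there is no secondary analysis. No mixed model, imputation or rule for a single missing reading appears anywhere.

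The sections on incomplete data do not agree:

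- 11.3 admits only participants who completed the whole protocol.
- 11.4.1 says "Incomplete data sets that contain only part of the protocol are included in the analysis as far as possible", and adds that nobody is recruited as a replacement.
- 11.5 has the data of anyone who does not finish destroyed and left out.
- 7.4, 8.5 and 9.1.6 use such data where they can, and 7.4 seeks a replacement.

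**The concern.** A repeated-measures MANOVA works on one row per participant and uses only full rows. For a nine-time outcome the row holds 2 x 9 = 18 readings. Someone who attends everything but has one failed pulse-oximeter, near-infrared, laser or capillary reading is dropped from that outcome, so the method works against 11.4.1 within that outcome. Settling the drop-out rules would not cure this, because it affects people who complete the protocol.

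Single failures are foreseeable. Section 9.2.2 repeats the physiological set every 5 minutes for 30 minutes after the cold bath, and blood saturation is read by finger clip in a protocol that cools a hand. The documents do not say which hand carries the clip.

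At stake are power in a study of 24 people and a different analysed set for each outcome. If failure is related to response, the comparison is also biased.

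**Working it through.** **Inputs.** N = 24 (11.2, synopsis); two-sided F-tests at 0.05 (11.4.2); 18 readings for the nine-time outcomes and 2 x 2 = 4 for the others (11.4.2). I count one terrestrial session, because 11.4.2 does not say which of the two is used, and I read the analysis as run outcome by outcome, in line with the hypotheses in 11.1. The missing-reading rate p is my assumption, with a range of 1 to 5%.

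**The plan's own figure.** Section 11.2 gives f(V) = 0.9, alpha 0.05, power 0.6, 3 groups, 14 measurements and a required N of 23. With p' = 13 contrasts, s = 2, df1 = 26, df2 = 2(N - 3 - 13 + 2) and noncentrality N x 2 x 0.9² = 1.62N, N = 23 gives df2 = 18, noncentrality 37.26 and power 0.647. N = 22 gives 0.586. So 23 is reproduced, but for a between-within design that is not the 2 x 9 within-participant analysis. No power is documented for the latter, so I use 60% at n = 24 as an assumed anchor.

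**Retention.** P(all 18 present) = (1 - p)^18, and the expected complete number is 24(1 - p)^18. At 1%: 24 x 0.835 = 20.0. At 5%: 24 x 0.397 = 9.5.

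**Power.** With n complete participants and q contrasts, the test is F(q, n - q) with noncentrality n x d².

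- Situation by time: q = 8. Power 0.60 at n = 24 requires d² = 0.656 (noncentrality 15.74).
- Situation: q = 1. Power 0.60 at n = 24 requires d² = 0.222 (noncentrality 5.34).

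Power is averaged over n ~ Binomial(24, P(complete)), and is zero when n ≤ q.

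| Missing rate | 1% | 2% | 3% | 5% |
|---|---|---|---|---|
| Complete of 24, 18 readings | 20.0 | 16.7 | 13.9 | 9.5 |
| Power, situation by time (8 df) | 0.453 | 0.322 | 0.217 | 0.077 |
| Power, situation (1 df) | 0.516 | 0.438 | 0.368 | 0.253 |
| Complete of 24, 4 readings | 23.1 | 22.1 | 21.2 | 19.5 |
| Power, 4 readings (1 df) | 0.581 | 0.562 | 0.543 | 0.506 |
| Complete of 24, whole sessions missing, 24(1 - p)² | 23.5 | 23.0 | 22.6 | 21.7 |
| Power, whole sessions missing (8 df) | 0.583 | 0.566 | 0.549 | 0.515 |

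At 5% scattered missing readings, P(n ≤ 8) = 0.338, and the 8-df multivariate test then cannot be computed.

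**Available-data model.** A simulation (1,500 runs per setting, compound-symmetric errors, same 60% anchor) gave situation-by-time power at 0, 1, 2 and 5% missing of 0.60, 0.44, 0.33 and 0.06 for the complete-case MANOVA. A repeated-measures model on all available readings gave 0.82, 0.82, 0.81 and 0.79. The higher level at 0% comes from the assumed covariance. The relevant evidence is that the second series hardly falls.

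**The case against.** **The conflict with 11.4.1 is limited.** A reader might infer that the undertaking in 11.4.1 cannot be kept at all. The documents do not support that. Its wording is qualified, exclusion is per outcome, and a participant with one failed reading still enters the other outcomes and the 2 x 2 analysis. The contradiction that is plain on the face of the text is between 11.3 and 11.5 on one side and 11.4.1, 7.4, 8.5 and 9.1.6 on the other. If 11.3 is read as demanding complete data sets, dropping such participants would even be the stated intent. This stands, and it means the rules must be reconciled as well as the method changed.

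**The loss is conditional.** A reader might infer that power collapses. No missing rate is documented, and the steep fall needs scattered, independent failures and concerns the 8-df test. The table shows how mild the loss is for whole sessions and for four readings. The visual check after collection in 12.2.4 may catch some failures, though it cannot recover a timed reading.

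**The simulated gap mixes two changes.** With a larger effect (multivariate power 0.79 with nothing missing), power at 3% missing was 0.30 for the complete-case multivariate test, 0.68 for a complete-case univariate repeated-measures ANOVA and 0.93 for the available-data model. Like for like, deletion costs 0.93 - 0.68 = 0.25. The other 0.68 - 0.30 = 0.38 comes from the choice of test, and the label in 11.4.2 does not settle which SPSS test is read. This also stands.

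**Bias.** A reader might infer a bias towards no difference. Response-related failure is plausible after a cold bath of the hand, but nothing in the documents fixes its size or direction.

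None of this changes the core fact: under the named method one missing reading of 18 removes the participant from that outcome, and the plan names nothing to prevent it.

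**Conclusion.** The point holds in this form. The nine-time analyses are complete-case per outcome, which sits badly with 11.4.1, and an available-data method avoids the loss at almost no cost. With independent failures at 1 to 5%, between 20.0 and 9.5 of 24 participants remain. Power falls from an assumed 60% to between 45 and 8% for situation by time, and to between 52 and 25% for the situation effect. These figures rest on the assumed failure rate, on independence and on an anchor borrowed from a different design. They show sensitivity and do not forecast what this trial will lose. The change should be made, but the point does not by itself invalidate the planned comparison.

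**What to change.** **Sections 11.4.2 and synopsis.** Make the primary analysis a linear mixed model per outcome (SPSS MIXED, restricted maximum likelihood). Use fixed situation, time and situation-by-time effects, a participant random effect, a pre-stated covariance structure for times within a session, and small-sample degrees of freedom that the SPSS version in use provides. The synopsis names V. 26 and 11.4.2 names V. 23, so state one. Fit it to all available readings, and use the same model for the two-time outcomes. Keep the complete-case MANOVA as a sensitivity analysis.

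**Sections 11.3, 11.4.1, 11.5 and 7.4, with 8.5 and 9.1.6.** Reconcile these so that partial data are kept and analysed under one rule. Say when a reading is set to missing (documented technical failure), and report participants and readings used per outcome.

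**Cost.** Wording only, with no new data, visits or participants. A covariance structure must be chosen in advance, and the model assumes readings are missing at random given those observed. That is weaker than the missing-completely-at-random assumption behind dropping incomplete participants.
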